7.2 Measures to Minimize Bias: Randomization and Blinding

Patients enrolling in trial will undergo permuted block randomization in groups of 4 at the time of enrollment. This will happen at the time of randomization using simple randomized opaque envelopes. Overall blinding is not feasible for this trial given that each arm features a different therapy administered in different departments of the hospital. Given that the primary endpoint is ORR at 6 months, a diagnostic radiologist reviewing for response (and DFS) will be blinded to the therapyarm.

7.3 **Concomitant Therapy**

No active systemic therapy for the treatment of HCC will be allowed from the time of enrollment to the time of primary outcome assessment. Expected supportive medication generally given as standard of care with either therapy arm will be allowed.

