3.0 STUDY DESIGN

The proposed study is a single site, prospective, randomized pilot study to assess the feasibility of recruitment of patients into a trial evaluating the efficacy and tolerability of selective transarterial Y90 radioembolization (radiation segmentectomy) versus stereotactic body radiation therapy (SBRT) for solitary early stage (≤ 3cm) hepatocellular carcinoma (HCC).

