5.3 Strategies for Recruitment

The majority of patients will be initially evaluated through the local liver tumor board. Currently, 1-2 patients who fit criteria are presented most weeks. It is estimated that around 50-60 patients in a year's time would be eligible. These patients will be set up to come to a multi-disciplinary clinic where they will have back-to-back clinic visits with both Interventional Radiology and Radiation Oncology on the same day. After both clinic visits are performed, a research coordinator (or if not available, an investigator) will approach eligible subjects and explain the trial and attempt enrollment. Direct referrals to either clinic who are eligible will also be seen by both specialties, and approached for the study, although this group will likely be much smaller than those discussed in tumor board.

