10.3 Sample Size Projections

The primary objective of the pilot study will be to access feasibility. 20 patients in total will be enrolled, with up to 10 patients per arm (depending on the amount of screen fails). These numbers should be sufficient for the assessment of feasibility.

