11.0 DATA SUBMISSION AND FORMS

REDCap (Research Electronic Data Capture) database system will be implemented to collect data for this study. The servers hosting REDCap are administered and supported by Indiana University's University Information Technology Services (UITS) and are physically located in IU's secured and environmentally structured data center on the IU Bloomington campus. To comply with HIPAA guidelines, physical, administrative, and technical safeguards and on ongoing risk management framework have been implemented and documented (NIST 800-53) to ensure the security and protection of the study data within the data center, the servers, and the database. REDCap is a software toolset developed by Vanderbilt University, with collaboration from a consortium of institutional partners, for electronic collection and management of research and clinical trial data. Indiana University has joined this consortium and has implemented REDCap within the Indiana University's central Information Technology Services (UITS) technical environment to enable rapid development and deployment of electronic data capture and reporting to support specific clinical and translational research projects. Access to the password-protected database will be limited to the investigators of this study, and any data that is distributed will be either de-identified or authorized by written permission from participants. All source documents are to remain in the patient's clinic file. All documents should be kept according to applicable federal guidelines. Clinical trial data in REDCap will be periodically monitored by the IU Simon Cancer Center Data Safety Monitoring Committee.

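### A single stated block size of 4 with opaque envelopes, at one unblinded site, lets a recruiter who tracks allocations deduce on average a third of them; varied blocks and independent custody would reduce this cheaply

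*Combined protocol and SAP*

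**What the plan says.** Section 3.0 describes a "single site, prospective, randomized pilot study". Section 10.3 plans that "20 patients in total will be enrolled, with up to 10 patients per arm".

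Section 7.2 gives the allocation method as "permuted block randomization in groups of 4 at the time of enrollment", carried out "using simple randomized opaque envelopes". It gives one block size and no stratification. It does not say whether the envelopes are sealed or sequentially numbered, who generates the list, or who holds and opens the envelopes. The same section states that "Overall blinding is not feasible for this trial". The bias protection it adds is that "a diagnostic radiologist reviewing for response (and DFS) will be blinded" to treatment arm.

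Under Section 5.3, "a research coordinator (or if not available, an investigator) will approach eligible subjects". Section 8.1 sets the order: tumor-board agreement that either treatment is viable, back-to-back visits with both specialties, approach straight after those visits, then enrolment and randomization if the patient agrees. Section 6.0 places consent before registration in OnCore. It does not say whether registration comes before the envelope is opened.

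**The concern.** At one site with open treatment and one unstratified sequence, earlier allocations can be seen by the people who recruit. If the block size is also fixed and printed in the protocol, the remaining places in a block can be worked out by subtraction. An opaque envelope hides the card inside it but does not prevent that deduction.

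The step exposed is the approach to the patient. Someone who expects a particular arm next could present the trial more or less warmly, or depart from the immediate-approach rule. Recruitment and refusal form the primary endpoint (Section 4.1), and the form in Appendix VI records reasons for refusing consent only, so an eligible patient who was never approached would leave no entry on it. Section 5.3 estimates 50 to 60 eligible patients a year for 20 places, so there would be room for selection. Selective entry would also weaken the comparability of the arms for ORR, toxicity and patient-reported outcomes, and Table 1 says that ORR may inform the sample size of the later trial.

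**Working it through.** **Inputs.** Block size 4 (Section 7.2); 20 patients, up to 10 per arm (Section 10.3). The 1:1 ratio is inferred from 10 per arm. The observer is assumed to know the block size, where each block starts and all earlier allocations.

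**The plan's own figures.** 20/4 = 5 complete blocks, giving exactly 10 per arm. This agrees with Section 10.3. The plan gives no figure for predictability.

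**Certain assignments, fixed blocks of 4.** There are 6 equally likely sequences.
- 2 sequences (both patients of one arm first) force positions 3 and 4.
- The other 4 force position 4 only.
- Expected forced per block = (2×2 + 4×1)/6 = 4/3, and (4/3)/4 = 33.3%.
- Over 5 blocks: 5 × 4/3 = 6.67 of 20.
- The count is 5 plus a binomial (5, 1/3) variable, so the range is 5 to 10 (25% to 50%). P(5) = 0.13, P(6) = 0.33, P(7) = 0.33, P(8 or more) = 0.21.

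**Best guess, fixed blocks of 4** (name the arm with more places left).
- Position 1: 1/2.
- Position 2: 2/3.
- Position 3: 1/3×1 + 2/3×1/2 = 2/3.
- Position 4: 1.
- Mean = (0.500 + 0.667 + 0.667 + 1)/4 = 70.8%, against 50% under simple randomization.

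**Alternatives at 20 patients.** The observer knows the possible sizes and updates on all earlier allocations.

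| Scheme | Certain | Best guess |
|---|---|---|
| Fixed 4 | 6.67 of 20 (33.3%) | 70.8% |
| Fixed 6 | 25% | 68.3% |
| 4 or 6, each chosen at random | about 1.2 of 20 (about 6%) | about 68.5% |
| 4, 4, 6, 6 in random order | about 13% | – |

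Because this observer knows the possible sizes, the table does not measure any further gain from keeping them undisclosed.

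**Balance at patient 20 with random 4 or 6.** The list ends on a block boundary with probability 0.40625. Otherwise patient 20 is:
- fourth in a block of 6 (probability 0.21875; unbalanced with probability 0.4);
- second in a block of 4 (0.1875; 1/3);
- second in a block of 6 (0.1875; 0.4).

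P(11/9) = 0.0875 + 0.0625 + 0.0750 = 0.225, about 23%. If accrual stops mid-block, the largest difference is 3 with a block of 6, against 2 with a block of 4.

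**The case against.** The strongest reply is that Section 8.1 already constrains the recruiter. Patients reach the approach only after the tumor board has accepted either treatment and both specialties have seen them. The approach follows at once, and randomization follows agreement. This stands, and it leaves little room to time an approach within the rules. What it leaves open is how the trial is presented, and departures from the immediate-approach rule.

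Second, deduction needs someone who follows the whole sequence and its block boundaries. The plan shows neither that recruiters do so nor that an independent person holds the envelopes. A reader might infer that a third of allocations simply are known in advance. The documents do not support that: one third is an average, conditional on such an observer.

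Third, a reader might infer that the recruitment endpoint or the arm comparisons are biased. That is not shown. Recruitment and screen failures are pooled over arms and summarized descriptively, and the arm comparisons come from 20 patients with no power claim. Guessing accuracy is not a shift in recruitment rate, and no such shift can be calculated from the documents. The blinded radiology reading protects assessment, though not allocation.

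Fourth, varied block sizes lower best-guess accuracy by only about 2 points, and steering needs a good guess rather than certainty. This also stands, and it is why changing the block size alone is not enough.

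**Conclusion.** The point holds as a design weakness with a cheap improvement. Followed as written, Section 7.2 leaves allocation deducible: on average 33.3% of assignments (6.7 of 20, range 5 to 10) and 70.8% correct guesses. This rests on 1:1 allocation and a recruiter who tracks past allocations and block boundaries. It is a risk of selection and no evidence of it, and the sequence in Section 8.1 reduces the risk without removing it.

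The replacement rule in Section 10.4 could add to the known allocations. It assigns a replacement to the RS arm without saying how that fits the block sequence; if the patient is placed there directly, that assignment is known in advance. This is conditional and is not counted in the figures above.

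**What to change.** For future patients, replace the fixed block of 4 with randomly varying sizes, for example 4 and 6, neither stated in the protocol nor disclosed to recruiting staff. Have someone outside the recruiting team generate the list and hold it, or hold sequentially numbered sealed envelopes, and open each one only after consent and registration. Section 8.1 already has randomization after agreement; the additions are the custody rule and the explicit order of registration before opening.

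The administrative cost is a new list and a revision of Section 7.2. The statistical cost is an 11/9 split in about 23% of lists at 20 patients, and a difference of up to 3 if accrual stops mid-block. If 10/10 matters, put two blocks of 4 and two of 6 in random order: 4 + 4 + 6 + 6 = 20, with about 13% of assignments certain. If patients have already been randomized, choose blocks that sum to the places remaining.

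Electronic allocation is possible but should not be assumed to be in place. Section 11.0 says that "REDCap (Research Electronic Data Capture) database system will be implemented to collect data for this study"; it does not describe allocation, and registration is in OnCore (Section 6.0).

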4.2 Secondary Objectives (SO)/ Secondary Endpoints (SE)

- SO: To compare the proportion of patients with toxicities (≥ grade 4) using CTCAE version 5.0 between RS and SBRT for patients with small (≤3 cm) solitary hepatocellular carcinoma (HCC). Only those toxicities at least possibly related to treatment will be considered.
 - **SE:** Laboratory (CBC, CMP, INR)/clinical toxicities measured using CTCAE version 5.0 up to 6 months post treatment.
- 2. **SO**: To compare the mean change in hepatobiliary function, as measured 3 months after treatment using a functional HIDA scan, between RS and SBRT for patients with small (≤3 cm) solitary hepatocellular carcinoma (HCC). SE: Change in % radiotracer extraction from baseline, on functional HIDA scan, 3 months after treatment
- 3. **SO:** To compare the mean change in patient-reported outcomes (PROs) from baseline, at 1, 3 and 6 months, between RS and SBRT, for patients with small (≤3 cm) solitary hepatocellular carcinoma (HCC), using FACT -G and COST FACIT questionnaires. **SE:** Change in FACT-G and COST FACIT from baseline at 1, 3 and 6 months
- 4. SO: To compare the disease-free survival (DFS) rates of RS and SBRT at 2 years using mRECIST on CT or MR for patients with small (≤3 cm) solitary hepatocellular carcinoma (HCC).SE: DFS at 2 years after treatment completion as measured with mRECIST on CT or MR
- 5. **SO:** To compare time-to-secondary treatment (TTST) between RS and SBRT for patients with small (≤3 cm) solitary hepatocellular carcinoma (HCC) up to 2 years after initial treatment. SE: TTST for target tumor up to 2 years following treatment.

6. **SO:** To measure the objective response rate (ORR) of radiation segmentectomy (RS) and stereotactic body radiation therapy (SBRT) as measured at 6 months using mRECIST (appendix IV) for patients with small (≤3 cm) solitary hepatocellular carcinoma (HCC) to better allow for an appropriately powered trial evaluating the efficacy of these treatments. **SE:** ORR at 6 months after completion of treatment using mRECIST on multiphase CT or MR.

Table 1: Justification for Endpoints

	OBJECTIVES	ENDPOINTS	JUSTIFCATION FOR ENDPOINTS		
Pri	mary				

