10.5.3 Analysis of the Secondary Endpoint(s)

The secondary research questions to be addressed are as follows:

- 1. To compare the proportion of any toxicities (≥ grade 4) using CTCAE between RS and SBRT for patients with small (≤3 cm) solitary hepatocellular carcinoma (HCC).
 - The proportion of patients with toxicities will be provided along with corresponding 95% confidence intervals. Toxicity rates will be compared using a Fisher's Exact Test.
- 2. To compare the mean change in hepatobiliary function, as measured 3 months after treatment using a functional HIDA scan, between RS and SBRT for patients with small (≤3 cm) solitary hepatocellular carcinoma (HCC).
 - A two-sample t-test will be used to analyze mean changes in liver function as measured by functional HIDA scan.
- 3. To compare the mean change in patient-reported outcomes from baseline, at 3 and 6 months, between RS and SBRT, for patients with small (≤3 cm) solitary hepatocellular carcinoma (HCC), using FACT-G and COST FACIT.
 - A two-sample t-test will be used to analyze mean changes in patient reported outcomes as measured using FACT-G and COST FACIT.
- 4. To compare the disease-free survival (DFS) rates of RS and SBRT at 2 years using mRECIST on CT or MR for patients with small (≤3 cm) solitary hepatocellular carcinoma (HCC).
 - DFS rates will be compared using Kaplan-Meier estimates with a log rank analysis.
- 5. To compare time-to-secondary treatment (TTST) between RS and SBRT for patients with small (≤3 cm) solitary hepatocellular carcinoma (HCC) up to 2 years after initial treatment.
 - TTST rates will be compared using Kaplan-Meier estimates with a log rank analysis.

6. The proportion of patients with ORR at 6 months will be provided along with corresponding 95% confidence intervals. ORR rates will be compared using a Fisher's Exact Test.

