10.5.4 Safety Analyses

Toxicity will be measured as a secondary outcome using CTCAE version 5.0. Adverse event monitoring will occur throughout the duration of the study and will be performed by research coordinators and investigators.

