13.1.3 Determining Attribution to the Intervention(s)

Attribution is an assessment of the relationship between the AE and the medical intervention. CTCAE does not define an AE as necessarily "caused by a therapeutic intervention". After naming and grading the event, the clinical investigator must assign an attribution to the AE using the attribution categories in Table 2 below.

Table 2: Determining Attribution

Relationship	Attribution	Description
Unrelated to investigational	Unrelated	The AE is clearly NO T related
intervention	Unlikely	The AE is doubtfully related
	Possible	The AE may be related
Related to investigational intervention	Probable	The AE is likely related
micer vention	Definite	The AE is clearly related

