13.3 Time Period and Frequency for Event Assessment and Follow-Up

The occurrence of an adverse event (AE) or serious adverse event (SAE) may come to the attention of study personnel during study visits and interviews of a study participant presenting for medical care or upon review of the medical record.

Adverse events will be recorded with start dates occurring any time after informed consent is obtained until 7 (for non-serious AEs) or up to 30 days (for SAEs) after the 6 month visit. At each study visit, the investigator will inquire about the occurrence of AE/SAEs since the last visit. Events will be followed for outcome information until adequate resolution or stabilization.

All AEs including local and systemic reactions not meeting the criteria for SAEs will be captured on the appropriate case report form (CRF). Information to be collected includes event description, time of onset, clinician's assessment of severity, relationship to study product (assessed only by those with the training and authority to make a diagnosis), and time of resolution/stabilization of the event. All AEs occurring while on study must be documented appropriately regardless of relationship. All AEs will be followed to adequate resolution.

Any medical condition that is present at the time that the participant is screened will be considered as baseline and not reported as an AE. However, if the study participant's condition deteriorates at any time during the study, it will be recorded as an AE.

Changes in the severity of an AE will be documented to allow an assessment of the duration of the event at each level of severity to be performed. AEs characterized as intermittent require documentation of onset and duration of each episode.

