13.4 REPORTING ADVERSE EVENTS

Adverse events will be recorded from the time of informed consent and for 30 days after the 6 month visit regardless of whether or not the event(s) are considered related to the study procedure. All AEs considered related to study procedures will be followed until resolution, return to baseline, or deemed clinically insignificant, even if this is after the 6 month visit Any death occurring within 30 days after intervention must be reported as an SAE regardless of attribution.

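### Section 4.2 limits the RS-versus-SBRT toxicity comparison to events called related without masking, the statistical sections do not, and attribution alone can shift the estimated difference

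*Combined protocol and SAP*

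**What the plan says.** Section 4.2 item 1 sets a between-arm comparison of the proportion of patients with grade 4 or higher toxicity up to 6 months after treatment, and adds a filter: "Only those toxicities at least possibly related to treatment will be considered". Section 10.5.3 item 1 makes this a formal test: "Toxicity rates will be compared using a Fisher's Exact Test". Section 10.2.2 states the hypotheses as equal versus not equal. Neither statistical section repeats the filter. Both, like the synopsis, speak of *any* toxicity of that grade.

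On who decides relatedness, 13.1.3 says that "the clinical investigator must assign an attribution to the AE using the attribution categories in Table 2 below". Section 13.3 asks for diagnostic authority but sets no masking condition. Adverse event monitoring, under 10.5.4, "will be performed by research coordinators and investigators".

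On masking, 7.2 says: "Overall blinding is not feasible for this trial given that each arm features a different therapy administered in different departments of the hospital". The protection it offers is for imaging: "a diagnostic radiologist reviewing for response (and DFS) will be blinded to the therapyarm". Section 8.1 likewise has the 6-month response read by two radiologists who do not know the treatment.

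On recording, 13.4 collects adverse events from consent until after the 6-month visit "regardless of whether or not the event(s) are considered related to the study procedure". Section 13.3 also requires events to be documented whatever their relationship.

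**The concern.** There are two linked problems. The first is that the endpoint has two readings. An analyst following 4.2 and one following 10.5.3 could count different patients from the same data, and nothing says which governs.

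The second arises if 4.2 governs. Counting then depends on a judgement made after randomisation, by someone who in all likelihood knows the arm. That judgement is hard in this population. Section 2.2 notes that most patients with HCC have chronic liver disease, and 2.3 lists worsening liver function as an expected toxicity of both treatments. A decompensation or a laboratory change could reasonably be put down to either. If events are called related more readily in one arm, the comparison measures that habit together with harm. Table 1 justifies the endpoint as a measure of damage to liver parenchyma, and the pilot is meant to prepare a larger trial, so the rates by arm are what will be carried forward.

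**Working it through.** **Step 1. The definitions side by side.**

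| Place | Grade | Relatedness condition |
|---|---|---|
| Synopsis, secondary objective 1 | 4 or higher | none; says *any* |
| 4.2 item 1 | 4 or higher | at least possibly related only |
| Table 1, item 1 | 4 or higher | none |
| 8.2 | 4 or higher | none |
| 10.2.2 item 1 | 4 or higher | none; says *any* |
| 10.5.3 item 1 | 4 or higher | none; says *any* |

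The filter is written once. *Any* could mean any type of event or any cause; no section says.

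**Step 2. What the filter removes.** In Table 2 of 13.1.3 the categories below possible are unrelated and unlikely. Only events placed there drop out.

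**Step 3. Size of the effect.** The plan gives no toxicity rate, effect size, power or alpha for this comparison, so it has no figure to reproduce. From 10.3, n = 10 per arm. Three inputs are assumed: an all-cause rate r, equal in both arms; a probability a that a qualifying event is called at least possibly related, 90% in one arm and 50% in the other; and one qualifying event per affected patient. Then

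counted rate = r × a, and spurious gap = r × (0.90 − 0.50).

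The chance of p ≤ 0.05 (two-sided Fisher, assumed level 0.05) comes from exact enumeration of two binomials with n = 10.

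| r | Counted rates | Gap | P(p ≤ 0.05), filtered | P(p ≤ 0.05), all-cause |
|---|---|---|---|---|
| 10% | 9% v 5% | 4 points | 0.06% | 0.1% |
| 20% | 18% v 10% | 8 points | 0.8% | 0.8% |
| 30% | 27% v 15% | 12 points | 2.3% | 1.2% |
| 50% | 45% v 25% | 20 points | 5.6% | 1.3% |

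The all-cause comparison has an expected gap of zero in every row. If every event were called related in one arm and none in the other, the chance of p ≤ 0.05 would be 0.2%, 3.3%, 15% and 62%.

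**Step 4. Why the p-value hardly moves.** With 10 per arm, 2 v 0 gives p = 0.47, 4 v 0 gives 0.087, and 5 v 0 (p = 0.033) is the smallest split against zero below 0.05. One reclassified patient moves an arm's rate by 1/10 = 10 points. The exact 95% interval is 0.3% to 44.5% for 1/10 and 2.5% to 55.6% for 2/10.

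**Step 5. The price of dropping the filter.** The standard error of the difference is √[(p₁(1−p₁) + p₂(1−p₂))/10].

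- r = 10%: filtered √[(0.09×0.91 + 0.05×0.95)/10] = 11 points; all-cause √[2×0.10×0.90/10] = 13 points.
- r = 20%: filtered √[(0.18×0.82 + 0.10×0.90)/10] = 15 points; all-cause √[2×0.20×0.80/10] = 18 points.
- r = 30%: filtered √[(0.27×0.73 + 0.15×0.85)/10] = 18 points; all-cause √[2×0.30×0.70/10] = 20 points.

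All-cause counting costs 2 to 3 points of standard error in these scenarios and removes a gap of 4 to 12 points. The confidence interval reflects the added noise. It does not reflect the bias.

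**The case against.** The strongest reply is that the sections defining the test carry no filter. If *any* means all-cause, the attribution problem disappears. That is fair, and for that reason the point cannot be put as a settled defect of the planned test. But no section says that attribution is ignored, and 4.2 is the only explicit rule, so the texts need reconciling on either reading.

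A reader might go further and infer that each department attributes its own patients' events, so that assessor and arm coincide. The documents do not support this. Section 7.1.2 has a clinician grade toxicity weekly during SBRT, but grading is not attribution. Section 8.2 has the principal investigator monitor safety, section 14 requires monthly team review, and serious events with their attributions go to the monitoring committee (13.4.2, 14.1, 14.5). None of that review is described as masked, but it is common to both arms. That attribution itself is unmasked is also an inference, from 7.2 and from the absence of any masked event review.

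A reader might also infer that the trial will report a false significant difference. Step 3 shows this to be unlikely unless events are common and attribution very unequal. The threshold is low, so the assumed contrast of 90% with 50% may be too large.

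Finally, randomisation balances background liver events only in expectation. With 10 per arm, chance imbalance can exceed the artefact (Step 5), and 10.4 removes and replaces RS patients found ineligible at the planning arteriogram. This stands as a limit on what either comparison can show. It is not a reason to add an avoidable bias.

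**Conclusion.** The point holds in two parts. The documents disagree on whether the toxicity comparison is filtered by relatedness. If the 4.2 rule is followed, the estimated arm difference can reflect attribution as well as harm, because no masked attribution is described and the underlying disease can explain the same events.

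The size is illustrative only: 4 to 12 points at equal all-cause rates of 10% to 30%, under an assumed 90% versus 50% attribution. Neither the rates nor the attribution probabilities are in the documents. The harm would be to the reported rates and intervals; in those scenarios the chance of p ≤ 0.05 stays between 0.06% and 2.3%. For one of six secondary endpoints in a 20-patient pilot sized for feasibility, this is a minor-to-moderate point. It is worth acting on because the correction is cheap.

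**What to change.** Amend 4.2 item 1 and align 10.2.2 item 1 and 10.5.3 item 1, so that all three define the between-arm comparison as patients with at least one grade 4 or higher event up to 6 months after treatment, regardless of attribution. Changing 10.5.3 alone would leave the restrictive sentence in 4.2 and turn an ambiguity into a contradiction. Bring the synopsis, Table 1 and 8.2 into line. Report the at-least-possibly-related count by arm beside the main comparison, as a descriptive supplement without a test.

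The cost is wording and one table row. No new data are needed, because 13.3 and 13.4 already require recording whatever the relationship. Those two sections end collection of non-serious events at different times (7 and 30 days after the 6-month visit), which touches either count alike. The downside is that background liver events add some noise at about 10 patients per arm, as shown in Step 5.
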